9.4 Follow-up of adverse events

All AEs will be followed until they have abated, or until a stable situation has been reached. Depending on the event, follow up may require additional tests or medical procedures as indicated, and/or referral to the general physician or a medical specialist. SAEs need to be reported until the end of the study within the Netherlands, as defined in the protocol

9.5 Data Safety Monitoring Board (DSMB) / Safety Committee

We will not install a DSMB as this study includes limited risks (see section 12).

10. STATISTICAL ANALYSIS

10.1 Analysis population

Full Analysis Set is defined as participants who have at least one available pair of algorithm generated output (either 6MWT distance estimator or TUG estimator) and in-clinic collection of ground truth (either 6MWT distance or TUG measured by clinicians). Participants from the Full Analysis Set will be used in analysis.

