- The table below illustrates the power achieved for a given algorithm performance assuming N=200 (including 25% drop-out) and a type I error of 0.05.

Table 1: Power Analysis with Various Modeling Assumptions

Success criteria	Current Performance	Power achieved(%)
ICC from free-living data based model		
>0.70	0.74	0.27
	0.76	0.50
	0.78	0.72
	0.79	0.82
ICC from virtual context-known data based model		
>0.75	0.78	0.23
	0.80	0.48
	0.82	0.75
	0.83	0.85

For PD

For our secondary endpoint, we performed a sample size calculation specifically for our PD cohort. This is an additional calculation to our primary sample size calculation which aims at the analytical validation of 6MWT distance measured with StudyWatch in clinic versus free living for COPD patients. This secondary sample size calculation was based on Intra-class correlation coefficient (ICC)¹⁹ between estimated walking measurements obtained from Study Watch data and StepWatch data in a free-living setting. Sample size calculations were derived from a total of 48 walking measurements estimating different aspects of walking behavior in an individual such as bouts of walking, bout speed, bout cadence, number of bouts, bout durations, and daily step counts.

Previous literature shows a range of minimum ICC values for walking related metrics in free living context.²³⁻²⁵ Not all metrics had known ICC. Generally an ICC ≥ 0.75 is considered excellent, 0.60–0.74 good, 0.40–0.59 fair, and <0.40 poor.²⁶ Minimum success criteria for the metrics, based on the literature, are listed in the following table.

All sample size calculations were based on a preliminary healthy cohort obtained from a

prior pilot study data that compared walking measurements obtained from Study watch compared with StepWatch in a free-living setting.

Based on the preliminary data collected, the following assumptions are made for sample size calculations:

- Each participant will have 2 pairs of data available (a pair consists of one algorithm estimated free living walking measurements from Study Watch and one from StepWatch)
- Minimum target performance based on free living data is different for each metric and thus are specified in the table below
- Since each of the free living metrics will be validated separately, no multiplicity is being considered, and each hypothesis test will be conducted with tolerance of 5% Type I error

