10.2 Primary Analysis

For COPD:

One of the primary objectives is to assess the validity of the free-living data based 6MWT distance estimator. The measurement agreement between the estimates from the free-living 6MWT distance Estimator and the in-clinic 6MWT distance measured by the test administrator will be assessed by Intra-class correlation (ICC) and is expected to be more than a clinically meaningful threshold. We define this clinically meaningful threshold with ICC success criteria and, for COPD population, ICC is 0.70. A test of equivalence, two one-sided test (TOST), will be used to assess the validity of the free-living data based 6MWT distance estimator. A Bland Altman plot will also be provided.

The other primary objective is to assess the validity of the virtual 6MWT distance estimator. We assume the model performance from virtual 6MWT will be higher than that of the free-living data based model, and the ICC threshold is >0.75 . A TOST procedure and a Bland Altman plot will also be used to assess the validity of the Virtual 6MWT distance estimator.

Considering that two co-primary endpoints will be validated separately, each TOST will be conducted at 5.0 level, without correction for multiplicity.

The algorithms are mainly developed using data collected from other sources, however, a small set of pre-selected data will be used to refine these algorithms prior to validation. As such, algorithm performance on this subset of data will not be included in the final validation analysis.

For PD:

The primary objective is to use collected data for future algorithm development. No formal performance evaluation will be conducted.

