10.3 Secondary Analysis

For COPD:

Intraclass correlation coefficient (ICC) and Bland Altman plots will be used to assess the validity of the free-living data based TUG time estimator and the Virtual TUG time estimator. ICC will be used to evaluate the agreement in free-living metrics between study watch and reference device (Step Watch). 41

The test-retest reliability of below algorithms will be assessed by looking at repeated estimates from the algorithm (e.g., week-over-week) and compared with the test-retest reliability of the in-clinic clinician measured 6MWT distance.

The algorithms are mainly developed using data collected from other sources, however, a small set of pre-selected data will be used to refine these algorithms.

For PD:

ICC will be used to evaluate the agreement in free-living metrics between study watch and reference device (Step Watch).

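### The single analysis set in section 10.1 is built on the wrong pair for the StepWatch agreement analyses, leaves the PD set undefined, and keeps tuning data in the secondary COPD analyses

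*Combined protocol and SAP*

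**What the plan says.** Section 10.1 names one set: "Full Analysis Set is defined as participants who have at least one available pair of algorithm generated output (either 6MWT distance estimator or TUG estimator"), matched with the clinician-measured 6MWT or TUG. It continues: "Participants from the Full Analysis Set will be used in analysis". No other analysis set is named. Section 10.4 summarises baseline characteristics in the same set, and disposition, device compliance and data availability in everyone enrolled.

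Section 10.3 then plans, for COPD and again for PD, an analysis that uses neither the estimators nor the in-clinic tests: "ICC will be used to evaluate the agreement in free-living metrics between study watch and reference device (Step Watch"). The PD cohort has its own calculation for this in section 4.4: "For our secondary endpoint, we performed a sample size calculation specifically for our PD cohort". There, "a pair consists of one algorithm estimated free living walking measurements from Study Watch and one from StepWatch".

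For the PD estimators, section 10.2 says "The primary objective is to use collected data for future algorithm development" and plans no formal evaluation of their performance.

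On the COPD data used to refine the algorithms, section 10.2 (primary analysis) states that "algorithm performance on this subset of data will not be included in the final validation analysis". Section 10.3 repeats that a pre-selected subset will refine the algorithms but does not repeat the exclusion.

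**The concern.** An analysis set should be entered through the data that its analysis needs. Here one set serves two kinds of analysis that need different data: estimator against in-clinic test, and Study Watch against StepWatch. Three consequences follow.

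- **PD StepWatch agreement.** A PD participant enters only if a 6MWT or TUG estimator has been run on that person's data. Whether and when that happens has no bearing on agreement between the two devices. It could leave the one analysis for which the PD cohort was sized with few participants or none.
- **COPD StepWatch agreement.** A participant with good concurrent wear but no estimator pair is left out for an unrelated reason.
- **Refinement subset.** These participants meet the entry rule. Where no later section removes them, an algorithm is assessed partly on data used to tune it, and agreement with the in-clinic test would be expected to look better than it is.

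The study aims to validate measures for use as trial endpoints, so the population for each agreement figure should be fixed before the data are seen.

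**Working it through.** **1. The two pairs side by side**

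| | Entry to the set (10.1) | What the StepWatch ICC needs (4.4, 10.3) |
|---|---|---|
| First member | 6MWT or TUG estimator output | Study Watch walking measurement at home |
| Second member | In-clinic 6MWT or TUG | StepWatch walking measurement at home |

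Neither pair implies the other. A set member without StepWatch data does no harm, because that person cannot contribute to the ICC. A person with StepWatch data who is outside the set is lost.

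**2. Reproducing the PD power table (Table 2 in section 4.4)**

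Inputs from section 4.4: N = 100 including 20% drop-out, so n = 100 × 0.80 = 80; type I error 0.05 per metric; success criterion r0 and current performance r1 as tabulated. The plan does not state the formula or whether the test is one- or two-sided. A one-sided Fisher z calculation with its small-sample term fits:

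power = Φ( [atanh(r1) + r1/(2(n − 1)) − atanh(r0)] × √(n − 3) − 1.645 )

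For the 95th percentile of cadence (r0 = 0.82, r1 = 0.88): atanh(0.88) = 1.3758, 0.88/158 = 0.0056, atanh(0.82) = 1.1568. The bracket is 0.2246; times √77 = 8.775 this is 1.971; less 1.645 it is 0.326; Φ(0.326) = 0.628.

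| Metric | r0 | r1 | Plan | Recomputed, n = 80 |
|---|---|---|---|---|
| Cadence, 95th percentile | 0.82 | 0.88 | 0.64 | 0.628 |
| Bout cadence, 75th percentile | 0.75 | 0.82 | 0.51 | 0.506 |
| Cadence, 75th percentile | 0.70 | 0.77 | 0.40 | 0.398 |
| Number of bouts | 0.66 | 0.70 | 0.17 | 0.170 |

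All four agree within 2 percentage points. Without the small-sample term the values are 0.609, 0.487, 0.381 and 0.161, slightly low. A two-sided test without that term gives 0.485, 0.364, 0.269 and 0.096, which does not fit. The table therefore rests on 80 people with Study Watch/StepWatch pairs, a condition that section 10.1 does not use.

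**3. What the written rule gives for PD**

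The number of PD participants with an estimator/in-clinic pair is not in the documents. The same formula over an assumed range:

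| PD participants in the set (assumed) | Cadence 95th | Bout cadence 75th | Cadence 75th | Number of bouts |
|---|---|---|---|---|
| 0 | no ICC can be estimated | – | – | – |
| 20 | 0.26 | 0.21 | 0.18 | 0.10 |
| 40 | 0.40 | 0.32 | 0.26 | 0.13 |
| 60 | 0.53 | 0.42 | 0.33 | 0.15 |
| 80 | 0.63 | 0.51 | 0.40 | 0.17 |

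**4. COPD**

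Home StepWatch wear falls between Visits 2 and 4. By Visit 2 a participant should have done the in-clinic tests at two visits and had about five weeks of Study Watch wear with weekly virtual tests. Having StepWatch pairs but no estimator pair should be uncommon. The documents give no count.

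**5. Refinement subset**

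| COPD analysis | Subset meets the 10.1 rule | Removed by a later section |
|---|---|---|
| 6MWT validation (10.2) | yes | yes |
| TUG validity (10.3) | yes | no |
| Test-retest (10.3) | yes | no |

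The subset is called small and its size is not given, so the upward bias in the TUG ICCs cannot be quantified.

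**The case against.** The strongest reply is that no analyst would read section 10.1 this way. The Summary sets the PD target as 100 complete cases with both devices at home, section 4.4 defines the device pair, and section 10.3 names the comparison, so the intended population is plain. That stands as evidence of intent. It does not replace a stated rule: using everyone with StepWatch data would depart from the only analysis set the plan names, with the choice made after data collection.

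A reader might infer something stronger: that no PD participant can qualify, so the PD set is certainly zero. The documents do not support that. Section 10.1 is not limited to COPD. Sections 1 and 2.1 have 6MWT algorithms developed on the PD data, and PD participants do the in-clinic tests and the weekly virtual tests that an estimator would need. No section says that an estimator will not be run on PD data, and none commits to running one. The count is undefined; zero is one possible value.

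A reader might also infer that tuning data enter the primary validation. They do not, because section 10.2 removes them. One could read that exclusion as covering every validation analysis, but it stands under the primary analysis, and section 10.3 restates the refinement without it.

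Two further replies stand. The COPD loss is probably small. The status of the PD ICC is itself unsettled: the Summary lists it as exploratory, section 8.1.2 says secondary endpoints do not apply to PD, and sections 4.4 and 10.3 treat it as secondary. This limits how much is lost but does not supply a population.

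**Conclusion.** The point holds as a wrong entry condition in a stated rule. It should be corrected, but it does not threaten the co-primary analyses.

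- **PD:** the set for the StepWatch ICC is undefined and could be empty, against 80 assumed in the power table. Power for the best-powered metric runs from 0.26 at an assumed 20 participants to 0.63 at 80. The PD baseline table in section 10.4 has the same problem.
- **COPD StepWatch ICC:** some participants are lost for an unrelated reason, probably few.
- **Refinement subset:** it stays in the TUG validity and test-retest analyses. Followed as written, the TUG ICCs would be biased upward by an amount that the documents do not allow one to compute.

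The power figures assume a one-sided test and the Fisher z form above, chosen because together they reproduce the plan's table. The PD counts below 80 are assumptions.

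**What to change.** Replace the single definition in section 10.1 with sets tied to the analyses:

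1. **COPD estimator validation sets**, one per estimator: at least one pair of that estimator's output and the matching in-clinic test, with the refinement subset excluded. State that the exclusion covers the 6MWT, TUG and test-retest analyses, and repeat it in section 10.3.
2. **StepWatch agreement sets**, one per cohort: at least one valid concurrent Study Watch/StepWatch pair at home. Summarise PD baseline characteristics in this set or in all enrolled.

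Disposition in everyone enrolled is already in section 10.4 and needs no change.

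In the same edit, reconcile the status of the PD ICC across the Summary and sections 4.4, 8.1.2 and 10.3. Also reconcile the PD numbers: 20% loss from 100 in section 4.4, 10% loss and 90 complete cases in the section on replacing withdrawn subjects (8.9), and up to 130 enrolled for 100 complete cases in the Summary.

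The cost is one paragraph in section 10.1, the matching sentence in 10.3, no new data, and slightly fewer participants in the TUG and test-retest analyses. With the PD set defined by device pairs and 80 available, power returns to the values in the plan's table.

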10.2 Primary Analysis

For COPD:

One of the primary objectives is to assess the validity of the free-living data based 6MWT distance estimator. The measurement agreement between the estimates from the free-living 6MWT distance Estimator and the in-clinic 6MWT distance measured by the test administrator will be assessed by Intra-class correlation (ICC) and is expected to be more than a clinically meaningful threshold. We define this clinically meaningful threshold with ICC success criteria and, for COPD population, ICC is 0.70. A test of equivalence, two one-sided test (TOST), will be used to assess the validity of the free-living data based 6MWT distance estimator. A Bland Altman plot will also be provided.

The other primary objective is to assess the validity of the virtual 6MWT distance estimator. We assume the model performance from virtual 6MWT will be higher than that of the free-living data based model, and the ICC threshold is >0.75 . A TOST procedure and a Bland Altman plot will also be used to assess the validity of the Virtual 6MWT distance estimator.

Considering that two co-primary endpoints will be validated separately, each TOST will be conducted at 5.0 level, without correction for multiplicity.

The algorithms are mainly developed using data collected from other sources, however, a small set of pre-selected data will be used to refine these algorithms prior to validation. As such, algorithm performance on this subset of data will not be included in the final validation analysis.

For PD:

The primary objective is to use collected data for future algorithm development. No formal performance evaluation will be conducted.

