4.4 Sample size calculation

The study plans to enroll 200 participants for COPD and 100 for PD. For the COPD cohort, the objective is to conduct analytical validation of algorithms that estimate in-clinic 6MWT distance based on free-living based data and virtual 6MWT context-known data. The algorithms are being developed based on the prior dataset from community-dwelling individuals in their usual state of health, including people with COPD.

For COPD

Sample size calculations were based on our co-primary endpoints of Intra-class correlation coefficient (ICC)²¹ between estimated 6MWT distance from free-living data and virtual 6MWT context-known data with in-clinic 6MWT distance. However, since free-living data is known to be less structured and may not involve walking for 6 minutes or any prolonged period, we expect to see lower performance from the free-living data based model compared to virtual context-known data based model. Previous literature²² shows a minimum ICC of 0.75 from virtual walk tests. Thus the minimum success criteria for virtual context-known algorithm was ICC >0.75 . For the IRL model the threshold was lowered to an ICC of >0.70 .

All sample size calculations were based on a preliminary COPD and healthy cohorts obtained from BHS (NCT03154346) data that predicts 6MWT distance from in-clinic context-known data and free-living data.

Based on the preliminary data collected, the following assumptions are made for sample size calculations:

- Each participant will have 2 pairs of data available (a pair consists of one algorithm estimated 6MWT distance and one clinician measured 6MWT distance)
- Model performance based on virtual context-known data will be higher than model based on free-living data
- Minimum target performance based on IRL data is ICC >0.70 . Minimum target performance based on virtual walk test data is ICC >0.75
- Since both free-living data based estimate and context-known data based estimate algorithms will be validated separately, no multiplicity is being considered, and each hypothesis test will be conducted with tolerance of 5% Type I error.

- About 75% of participants will have sufficient data for the final algorithm assessment. (This takes into consideration participants' drop outs, sensor data of insufficient quality to generate reliable algorithm outputs, and failure to obtain the ground truth labels (e.g. clinician evaluation of 6MWT distance))

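### Both co-primary endpoints are to be tested by TOST, but the only success criterion is a lower ICC threshold, and no TOST parameter or margin is given

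*Combined protocol and SAP*

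**What the plan says.** Section 10.2 assesses agreement by ICC, which is to lie above a threshold. For the free-living estimator: "We define this clinically meaningful threshold with ICC success criteria and, for COPD population, ICC is 0.70". For the virtual estimator the threshold is above 0.75. The tests named are "A test of equivalence, two one-sided test (TOST), will be used to assess the validity of the free-living data based 6MWT distance estimator" and "A TOST procedure and a Bland Altman plot will also be used to assess the validity of the Virtual 6MWT distance estimator". On the error level, "each TOST will be conducted at 5.0 level, without correction for multiplicity". No other test is named for either co-primary endpoint.

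Section 4.4 bases the sample size on the ICC and repeats both thresholds, for example "Thus the minimum success criteria for virtual context-known algorithm was ICC >0.75". It adds that "each hypothesis test will be conducted with tolerance of 5% Type I error". It mentions neither TOST nor equivalence and does not give the sidedness of the test. Table 1 gives power "assuming N=200 (including 25% drop-out) and a type I error of 0.05".

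The endpoint itself is described in two ways. Section 8.1.1 uses agreement or ICC; the Summary uses the difference between the in-clinic distance and the estimate.

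**The concern.** TOST needs a parameter and two limits, and it concludes that the parameter lies between them. The criterion in 10.2 has only a lower limit, and a very high ICC would not count against the algorithm. No upper ICC limit and no margin in metres appears anywhere in the protocol. MCID is in the abbreviation list but has no value and is not used.

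An analyst therefore has to choose between two readings. Under the first, TOST is a misnomer for a one-sided test of the ICC against its threshold, and the decision rule must be inferred from 4.4 and Table 1. Under the second, suggested by the Summary's endpoint wording, TOST is applied to the mean difference. That checks average bias only, with a margin not fixed in advance and no power calculation behind it. These are the only tests behind the two co-primary conclusions, so the choice should not be open once data are available.

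**Working it through.** **Step 1: which test does Table 1 describe?** Inputs from 4.4: thresholds r0 = 0.70 and 0.75, the true ICCs r1 in Table 1, type I error 0.05, and 200 enrolled with 25% loss, so n = 0.75 × 200 = 150. Section 8.9 on replacement also aims for 150 complete COPD cases. I assume one algorithm–clinician pair per participant. Section 4.4 mentions two pairs but gives no within-participant correlation.

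One-sided power = Φ[(atanh r1 − atanh r0) × √(n − 1.5) − 1.645].

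Example, r0 = 0.70, r1 = 0.79, n = 150: (1.0714 − 0.8673) × √148.5 − 1.645 = 0.2041 × 12.186 − 1.645 = 0.842, and Φ(0.842) = 0.80. Table 1 states 0.82.

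The last column replaces 1.645 by 1.96 (two-sided 5%).

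| Threshold | True ICC | Table 1 | One-sided, n=150 | One-sided, n=160 | Two-sided, n=150 |
|---|---|---|---|---|---|
| 0.70 | 0.74 | 0.27 | 0.264 | 0.275 | 0.172 |
| 0.70 | 0.76 | 0.50 | 0.471 | 0.491 | 0.349 |
| 0.70 | 0.78 | 0.72 | 0.700 | 0.725 | 0.583 |
| 0.70 | 0.79 | 0.82 | 0.800 | 0.823 | 0.701 |
| 0.75 | 0.78 | 0.23 | 0.223 | 0.232 | 0.141 |
| 0.75 | 0.80 | 0.48 | 0.455 | 0.475 | 0.334 |
| 0.75 | 0.82 | 0.75 | 0.724 | 0.749 | 0.610 |
| 0.75 | 0.83 | 0.85 | 0.836 | 0.856 | 0.746 |
| Largest miss | | | 0.029 | 0.009 | 0.151 |

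An F test with n − 1 and n degrees of freedom agrees with the one-sided columns within 0.002. The best one-sided fit is n = 161 (largest miss 0.008). For the two-sided test, the best fit over n = 100 to 399 is n = 222 with a largest miss of 0.042, and 222 is more than the 200 to be enrolled. Table 1 is thus close to a one-sided 5% test of the ICC against its threshold, with no upper limit involved. The match at 150 is close, not exact. The protocol gives no formula, so I do not treat the gap as an error.

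**Step 2: what that rule requires.** Smallest passing observed ICC = tanh[atanh r0 + 1.645/√(n − 1.5)]. At n = 150 and r0 = 0.70: tanh(0.8673 + 0.1350) = 0.763. At r0 = 0.75: tanh(0.9730 + 0.1350) = 0.803.

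| n | Free-living | Virtual |
|---|---|---|
| 130 | 0.767 | 0.807 |
| 140 | 0.765 | 0.805 |
| 150 | 0.763 | 0.803 |
| 160 | 0.761 | 0.802 |

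The range of n is an assumption. Section 10.2 removes a refinement subset of unstated size, since "algorithm performance on this subset of data will not be included in the final validation analysis".

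**Step 3: can the other reading change the conclusion?** The protocol gives no SD and no margin, so this is illustration only. Assume n = 150, zero mean bias and a total SD V of 80 to 120 m. The SD of the difference is s = V × √[2(1 − ICC)], and TOST power = 2Φ(m√n/s − 1.645) − 1 for margin m, set to 0 when negative.

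- ICC 0.50, which fails both thresholds: s = 80 to 120 m. With m = 30 m, TOST passes with probability >0.99 at V = 80 and 0.84 at V = 120.
- ICC 0.79: s = 51.8 to 77.8 m. With m = 10 m, TOST passes with probability 0.53 at V = 80 and 0 at V = 120.

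**The case against.** The strongest reply is that the intent is clear. A 5% TOST consists of two one-sided 5% tests. Applied to the ICC, with no upper limit below 1, its upper arm never binds, and what remains is the one-sided test that Table 1 powers. Sections 4.4 and 8.1.1 both name the ICC, and only the Summary points to a difference. On this view the harm is a wrong name. That is fair as an account of what was probably meant, and it is why the point is not graded higher. But it requires the reader to supply the parameter and drop half of the named procedure, and 10.2 licenses neither.

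Three narrower objections also deserve weight. First, the gap between the threshold and the smallest passing ICC is the ordinary gap between a point estimate and a test, and naming TOST does not cause it. This stands. It matters here only because 10.2 does not say whether the estimate or a confidence limit must exceed the threshold. Second, the cut-offs assume one pair per participant. Treating 300 pairs as independent would give about 0.745 and 0.789; that extreme does not fit Table 1, but the dependence is real. Third, the ICC form and the handling of repeated pairs are also unspecified. They need settling too, but are separate points.

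**Conclusion.** The concern holds and should be fixed. The only test named for the co-primary endpoints does not match their only success criterion, and it lacks the parameter and limits needed to run it. Under the best-supported reading, the consequence is a misnamed primary test and a decision rule that must be inferred. An observed ICC of about 0.70 to 0.76 (free-living) or 0.75 to 0.80 (virtual) would then be above the threshold in 10.2 yet fail the test that Table 1 powers. Under the mean-difference reading, the margin is not fixed in advance, Table 1 does not apply, and the conclusion could be reversed.

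The mismatch in 10.2 rests on the text alone. The cut-offs rest on about 150 validated participants with one pair each. The reversal rests on assumed SDs and margins.

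**What to change.** In 10.2, replace both TOST sentences with: *H0: ICC ≤ 0.70 (free-living) and H0: ICC ≤ 0.75 (virtual), each tested at the one-sided 5% level; success if the lower limit of the one-sided 95% confidence interval for the ICC exceeds the threshold.* In the error-level sentence, refer to each test instead of each TOST, and give the level as one-sided 5%. Change the co-primary endpoints in the Summary to the ICC wording of 8.1.1. Keep the Bland-Altman plots as supporting output.

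If the sponsor also wants a TOST on the mean difference as a check for bias, label it supportive and state its margin in metres before the data are analysed. If it is to be confirmatory, give its power as well.

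The cost is a wording change in 10.2 and the Summary, with no new data. Table 1 can stand. A new power calculation is needed only if a mean-difference TOST becomes confirmatory.
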